5. SUBJECT ENROLLMENT

Before subjects may be entered into the study, Amgen requires a copy of the site's written IRB approval of the protocol, ICF, and all other subject information and/or recruitment material, if applicable (see [Section 11.2](#)). All subjects must personally sign and date the ICF before commencement of study-specific procedures. All subjects who enter into the screening period for the study (defined as the point at which the subject signs the ICF) will receive a unique subject identification number assigned manually before any study-related activities/procedures are performed. This number will be used to identify the subject throughout the clinical study and must be used on all study documentation related to that subject. Subjects may be rescreened at the discretion of the investigator in consultation with Amgen. A subject is considered enrolled when the investigator decides that the subject has met all eligibility criteria. The investigator is to document this decision and date in the subject's medical record and in/on the enrollment case report form (CRF).

The subject identification number must remain constant throughout the entire clinical study; it must not be changed at the time of rescreening, enrollment, or randomization.

This number will not necessarily be the same as the randomization number assigned for the study. [REDACTED]

[REDACTED]

The Investigator is to document the enrollment decision and date, in the subject's medical record and in/on the enrollment CRF.

5.1 Randomization/Treatment Assignment

Subjects will be randomized by IVR/IWR in a 3:1 ratio to either TIW IV etelcalcetide or placebo in a double-blind manner prior to the Day 1 activities. The randomization number will be provided to the unblinded pharmacist by accessing the IVR/IWR and then the unblinded pharmacist will obtain the appropriate IP/Placebo box. Details for this

procedure will be provided in the IVR/IWR manual. In the event subjects are randomized, but are withdrawn before receiving study medication, a replacement subject may be enrolled in the subject's place and assigned to receive the identical treatment as the replaced subject.

The randomization date is to be documented in the subject's medical record and on the enrollment CRF.

5.2 Site Personnel Access to Individual Treatment Assignments

An unblinded pharmacist at the research facility (and/or their qualified designee) will have access to subjects' treatment assignment and will be responsible for preparing the appropriate treatment based on the randomized treatment provided by the IVR/IWR. Access to the randomization list or unblinded safety records will be limited to the unblinded pharmacist and/or their qualified designee. A subject's treatment assignment should only be unblinded when knowledge of the treatment is essential for the further management of the subject or may potentially impact the safety of subjects currently enrolled or subjects enrolled in the future.

Unblinding at the research facility for any other reason will be considered a protocol deviation. The investigator is strongly encouraged to contact the Amgen study manager before unblinding any subject's treatment assignment, but must do so within 24 hours after the event.

6. TREATMENT PROCEDURES

6.1 Classification of Product(s) and/or Medical Device(s)

The Amgen Investigational Product and placebo used in this study are AMG 416, also known as KAI-4169, and placebo. The Investigational Product Instruction Manual (IPIM), a document external to this protocol, contains detailed information regarding the storage, preparation, and administration of AMG 416 and placebo.

6.2 Investigational Product

Investigational product will be administered at the research facility by a qualified staff member. A physician, trained healthcare provider or qualified designee must be available at the time of administration of investigational product.

6.3 Amgen Investigational Product AMG 416

AMG 416 will be manufactured and packaged by Amgen Inc. or its designee, and distributed using Amgen clinical investigational product distribution procedures. The

active pharmaceutical ingredient (API) in AMG 416 is an eight-amino acid synthetic peptide prepared as a hydrochloride salt.

The AMG 416 investigational drug is supplied as a sterile, preservative-free, aqueous solution containing 10 mg AMG 416 API, [REDACTED] mg sodium chloride and [REDACTED] mg succinic acid, in a single-use 3 mL glass vial. The drug product vial contains 2 mL of clear, colorless solution with AMG 416 concentration of 5 mg/mL. The solution is ready to administer and has pH between [REDACTED] and [REDACTED]. The recommended storage condition for AMG 416 liquid drug product is between [REDACTED]°C to [REDACTED]°C.

Placebo will be presented in identical containers and stored/packaged in the same manner as AMG 416. Placebo is supplied as a sterile, preservative-free, aqueous solution containing [REDACTED] mg sodium chloride and [REDACTED] mg succinic acid, in a single-use 3 mL glass vial. The placebo vial contains 2 mL of clear, colorless solution. The solution is ready to administer and has pH between [REDACTED] and [REDACTED]. The recommended storage condition for the placebo drug product is [REDACTED]°C to [REDACTED]°C. Additional details regarding AMG 416 and placebo are provided in the IPIM.

6.3.1 Dosage, Administration, and Schedule

Each subject will receive twelve intravenous doses of 5 mg AMG 416 or placebo administered by bolus injection into the venous line of the dialysis circuit at the end of each of the 12 consecutive hemodialysis treatments, just prior to or during rinse-back with each hemodialysis session (ie, one dose per hemodialysis session, see [Section 7.2](#)).

The end of hemodialysis treatment is defined as the time at which the prescribed hemodialysis treatment has been completed (ie, remaining time on dialysis is zero) or when the arterial flow is stopped (eg, arterial line is clamped or disconnected to discontinue treatment), whichever occurs first.

After investigational product (IP) administration has been completed by a qualified healthcare professional, subjects will be observed for at least 30 minutes.

The date, time, package lot number, and quantity administered will be recorded on the individual subject's Investigational Product Administration CRF prior to database lock.

The effects of overdose of AMG 416 are not known. All overdose occurrences must be documented and corresponding adverse events must be recorded on the appropriate CRF and in the source documents.

6.3.1.1 Dosage Adjustments, Delays, Rules for Withholding or Restarting, Permanent Discontinuation

Subjects will be treated with investigational product thrice weekly for 4 weeks. The dose of investigational product is 5 mg. Dosing will be stopped or modified by the investigator and Amgen Medical Monitor if suspected adverse drug reactions, changes in vital signs, physical examination, or clinical laboratory results are observed and these changes pose a significant health risk. Clinically or medically significant suspected adverse drug reactions, and serious adverse events considered to be related to study procedures will be followed until resolved or considered stable.

The study may be terminated at any point in time at the discretion of the sponsor.

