The date and time of hemodialysis treatment will be recorded throughout the treatment period. When a visit corresponds to a dialysis day, study procedures should be completed prior to hemodialysis.

Following completion of all study procedures on Day 1, subjects will be discharged with instructions to return to the research facility at specified time points for dosing, collection of blood samples for PK, PD and completion of safety assessments (including blood samples for antibody analysis) through the end of the study according to the schedule of assessments.

- Other Predialysis Assessments after Day 1:
 - Body Weight (before dialysis) on Days 29 and 55
 - Physical exam on Days 15, 29 and 55
 - Vital signs (BP,HR,RR, TEMP) – all visits
 - 12 lead Electrocardiograms (ECG) on Day 28 and Day 55 (EOS)
 - Adverse event monitoring (including serious adverse events and deaths) – all visits
 - Concomitant medications – all visits
 - Pregnancy test on Day 34
 - Hematology, PT, aPTT on Days 15, 29 and 55
 - Clinical Chemistry on Days 15, 29 and 55
 - Albumin on Days 3, 8,15, 22, 27, 29, 34, 41, 55
 - Phosphorus on Days 3, 8, 15, 22, 27, 34, 41, 55
 - Calcium (cCa) on Days 8, 15, 22, 27, 29, 34, 41, 55
 - iPTH on Days 8, 15, 22, 27, 34, 41, and 55
 - Anti-Drug Antibodies on Day 29 and 55

Subjects will be followed for safety throughout the 4-week treatment period and for 4 weeks after the last dose of investigational product to Day 55 (EOS). Dosing with investigational product may be suspended, for low predialysis iPTH or cCa, symptomatic hypocalcemia, or other drug-related adverse events.

Subjects who test positive for antibodies to AMG 416 at the EOS visit will be asked to return for additional follow-up testing (see [section 7.4](#))

If there is a clinically significant clinical or laboratory abnormality that requires monitoring, subjects will be followed until resolution of the abnormality or until it is considered stable.

Subject participation is complete once Day 55 end-of-study (EOS) procedures are performed.

For a full list of study procedures, including the timing of each procedure, please refer to the [Schedule of Assessments](#).

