9.2 Reporting of Adverse Events

9.2.1 Reporting Procedures for Adverse Events That do not Meet Serious Criteria

The investigator is responsible for ensuring that all adverse events observed by the investigator or reported by the subject that occur from the dose of investigational product (AMG 416) through the Day 55 EOS are reported using the applicable CRF (eg, Event CRF).

The investigator must assign the following adverse event attributes:

- adverse event diagnosis or syndrome(s), if known (if not known, signs or symptoms)
- dates of onset and resolution (if resolved)
- severity [and/or toxicity per protocol]
- assessment of relatedness to AMG 416 or other therapies,
- action taken

The adverse event grading scale used will be the CTCAE version 4. The grading scale used in this study is described in [Appendix A](#). The criteria for grade 4 in the CTCAE grading scale differs from the regulatory criteria for serious adverse events. It is left to the investigator's judgment to report these grade 4 abnormalities as serious adverse events.

The investigator must assess whether the adverse event is possibly related to the investigational product. This relationship is indicated by a "yes" or "no" response to the question: "Is there a reasonable possibility that the event may have been caused by the investigational product?"

The investigator must assess whether the adverse event is possibly related to any study mandated activity (eg, protocol-required procedure (including any screening procedure[s])). This relationship is indicated by a "yes" or "no" response to the question: "Is there a reasonable possibility that the event may have been caused by a study activity, and/or procedure?"

The investigator is responsible for reviewing laboratory test results and determining whether an abnormal value in an individual study subject represents a clinically significant change from the subject's baseline values. In general, abnormal laboratory

findings without clinical significance (based on the investigator's judgment) are not to be recorded as adverse events. However, laboratory value changes that require treatment or adjustment in current therapy are considered adverse events. Where applicable, clinical sequelae (not the laboratory abnormality), are to be recorded as the adverse event.

If the severity of an adverse event changes from the date of onset to the date of resolution, record as a single event with the worst severity on the Event CRF.

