9.3 Changes in Serum Calcium and Symptomatic Hypocalcemia

Investigators should assess subjects for the onset of signs and symptoms associated with low serum calcium (see [Section 6.3.1.1](#)) at each visit. When observed,

“hypocalcemia” should be reported as the adverse event, and the associated signs and symptoms will also be captured.

Any serum calcium (corrected) (cCa) ≥ 7.5 and < 8.3 mg/dL can be reported as low blood calcium; however, low a calcium result does not need to be reported as an adverse event if no action is taken, and the value is not deemed clinically significant by the investigator. If the cCa is < 8.3 mg/dL and there are symptoms of hypocalcemia then the event is to be reported as hypocalcemia and considered a serious adverse event. The associated signs and symptoms should also be captured.

Also, any cCa level < 7.5 mg/dL is to be reported as a serious adverse event of low blood calcium if there are no associated signs and symptoms, but it is to be reported as hypocalcemia if there are associated symptoms. The associated signs and symptoms should also be captured.

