The AMG 416 phase 2 clinical program included a 4-week, double-blind, randomized, placebo-controlled study (Study 20120330 also known as KAI-4169-003) and a 12-week, open-label, dose-titration study (Study 20120331 also known as KAI-4169-005); both were conducted in hemodialysis subjects with SHPT, and the results are summarized in the Investigator's Brochure. Treatment with AMG 416 appeared to be generally safe and well-tolerated. The incidences of nausea, vomiting, or diarrhea were low and similar in subjects receiving AMG 416 or placebo. Serum iPTH levels decreased by 36.7% and 76.9%, respectively, from baseline values at the end of treatment among subjects given 5 or 10 mg doses of AMG 416. The reductions were significantly different in both dosage cohorts compared with placebo ($p < 0.01$ for both). Reductions in $iPTH \geq 30\%$ from baseline occurred in 53.9% of subjects treated with 5 mg and in 76.2% of those treated with 10 mg of AMG 416, compared with 15.4% ($p = 0.10$) and 9.5% ($p < 0.0001$) of those given placebo. Dose-dependent reductions in serum calcium also were observed. There were no treatment-emergent (developing) antibody responses detected against AMG 416 following up to 4 weeks of dosing in hemodialysis subjects with SHPT. Pre-existing antibodies against AMG 416 were detected in 1 subject not previously exposed to AMG 416.

In a 12-week, single-arm, open-label, dose titration phase 2 study among hemodialysis subjects with SHPT, 5 mg was given thrice weekly during hemodialysis with subsequent dose increases to 10 mg after 4 weeks of treatment, and up to 15 mg or 20 mg after 8 weeks of treatment based upon serial measurements of iPTH and cCa the week before dose titration. Doses were reduced for low iPTH or low cCa. Thirty-seven subjects were enrolled in the study and 5 discontinued the study early. Three treatment-emergent serious adverse events were reported, but none were considered to be related to study drug. The final dose of AMG 416 ranged from 2.5 mg to 20 mg after 12 weeks. The mean reduction in iPTH at the end of the 12-week treatment period was 53%; furthermore, 82% of the subjects achieved a reduction in iPTH $\geq 30\%$ at 12 weeks. The decreases in serum cCa were well tolerated, but 35% of subjects had 1 or more values of serum cCa < 8.0 mg/dL, and 2 subjects (5%) had 1 or more values of cCa < 7.5 mg/dL during treatment.

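### AE status of an asymptomatic cCa of 7.5 to < 8.3 mg/dL depends partly on investigator practice, no planned table counts subjects by the SAP's own cCa bands, and the first on-drug calcium is Day 8

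*Protocol*

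**What the plan says.** **Dosing.** Protocol 6.3.1.1 is headed as the rule for withholding and restarting. Its trigger closes with "or clinical laboratory results are observed and these changes pose a significant health risk", and the decision lies with the investigator and the sponsor's Medical Monitor. It has no cCa value and no condition for resuming, and nothing in it is marked as blacked out. The synopsis and 7.2.3 allow suspension for low cCa, and Table 1b footnote d says that cCa guides dosing at the next dialysis. None of them gives a number. Section 9.3 refers back to 6.3.1.1 on signs and symptoms of low calcium, but 6.3.1.1 has no calcium content.

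**Reporting.** For cCa of 7.5 to < 8.3 mg/dL, 9.3 says that a low result "does not need to be reported as an adverse event if no action is taken" and the investigator does not consider it clinically significant. Section 9.2.1 adds that "laboratory value changes that require treatment or adjustment in current therapy are considered adverse events". Two cases are fixed. In 9.3, "any cCa level < 7.5 mg/dL is to be reported as a serious adverse event of low blood calcium" when there are no symptoms, and any cCa below 8.3 with symptoms is a serious event of hypocalcemia.

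**Analysis.** SAP 5.4 sets three bands on measured cCa: < 7.0, 7.0 to < 7.5, and 7.5 to < 8.3 mg/dL. SAP 9.6.1 tabulates reported AEs. SAP 9.6.2 summarizes cCa by visit and arm, with change from baseline as an option.

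**Sampling.** Protocol 7.2.3 lists "Albumin on Days 3, 8,15, 22, 27, 29, 34, 41, 55" but "Calcium (cCa) on Days 8, 15, 22, 27, 29, 34, 41, 55".

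**The concern.** AE incidence is a secondary endpoint (10.1.1.2), and hypocalcemia heads the important identified risks in 2.3. Sites are multiple (3.2). If two subjects have the same asymptomatic value in the 7.5 to < 8.3 band, one may count as an AE and the other not, because one investigator adjusted therapy and the other did not. That part of the count would then mix drug effect with local habit, and the planned laboratory summaries do not supply the missing figure.

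The sampling point is separate. Section 2.3 relies on close monitoring to mitigate hypocalcemia, yet no calcium is scheduled between the first dose and Day 8.

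**Working it through.** **1. The plan's own safety figures.** Protocol 10.2 uses P(at least one case in 24) = 1 − (1 − p)^24. For p = 1% this is 1 − 0.99^24 = 0.214, and for p = 15% it is 1 − 0.85^24 = 0.980. Both match the stated 21% and 98%. The formula takes an event to be recorded whenever it occurs.

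**2. AE status by measured value, from 9.3 and 9.2.1.**

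| cCa (mg/dL) | Symptoms | Action taken or judged significant | Status |
|---|---|---|---|
| < 7.5 | either | irrelevant | SAE |
| 7.5 to < 8.3 | yes | irrelevant | SAE |
| 7.5 to < 8.3 | no | yes | AE |
| 7.5 to < 8.3 | no | no | need not be an AE |

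Only the last two rows depend on the investigator.

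**3. How many subjects might fall there.** The documents give no cCa distribution for 5 mg over 4 weeks. The nearest data are in the replaced text of 2.2.2 in the Amendment 3 summary of changes, used here only as historical data. In a 12-week phase 2 titration study (37 enrolled, final doses up to 20 mg), "35% of subjects had 1 or more values of serum cCa < 8.0 mg/dL". For the lower limit of 7.5 mg/dL, the same text gives two subjects, or 5%.

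- Counts: 13/37 = 0.351 and 2/37 = 0.054, so 11/37 had a lowest value of 7.5 to < 8.0.
- At the 12-week rate: 24 × 11/37 = 7.1 subjects.
- Scaled to 4 of 12 weeks at constant hazard (an assumption): 1 − (1 − 0.351)^(1/3) = 0.134 and 1 − (1 − 0.054)^(1/3) = 0.018. The difference is 0.116, and 24 × 0.116 = 2.8 subjects.

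Symptomatic cases are not removed. Four subjects in that study reported symptomatic hypocalcemia; if all four lay in this range, 7.1 falls to 24 × 7/37 = 4.5. Doses above 5 mg also make these rates too high for this trial. Leaving out 8.0 to < 8.3 makes them too low.

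**4. When withholding can decide AE status.** By footnote d a result acts at the next dialysis, and the last dose is Day 27. Of the eight post-dose calcium days in 7.2.3, only Days 8, 15 and 22 precede a dose at the next dialysis (Days 10, 17 and 24). For the other five, status turns on treatment or on judged significance.

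**5. First effect on dosing.** A Day 8 predialysis result acts on Day 10. Doses already given are Days 1, 3, 6 and 8, which is 4 of 12. The clinical chemistry panel adds nothing earlier, since after Day 1 it is drawn on Days 15, 29 and 55. A Day 3 calcium would act on Day 6, after Days 1 and 3, which is 2 of 12.

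**6. What the planned outputs show.** A by-visit mean, median or range does not give the number of distinct subjects below a limit at any time. The AE tables give only what was reported.

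**The case against.** A reader might infer that low-calcium AE incidence as a whole follows each investigator's own cut-off. The documents do not support that. The two clinically serious rows of the table are reported whatever is done. The Medical Monitor shares decisions to stop or modify dosing, which limits variation between sites. Investigators are blinded (10.3), so there is no clear reason to expect a shift favouring one arm, and the AE tables are descriptive.

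Measured cCa is also a secondary endpoint in its own right (10.1.1.2), drawn on a fixed schedule. Protocol 10.5.6 provides subject-level listings with out-of-range values flagged, and SAP section 10 declares no change to protocol-specified analyses. With about 32 subjects, someone could count low values by hand. SAP 5.4 states that its bands will be used to identify cases, and SAP Appendix A mentions laboratory shift grading. This largely stands: the information is collected and not lost. What is missing is a named output. No part of SAP section 9 calls for a count by band or a shift table, and a reference-range flag need not coincide with 8.3 mg/dL.

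On monitoring, 9.3 requires assessment for signs and symptoms of low calcium at each visit, 7.3.10 allows extra safety tests, and 4.2.1 excludes subjects with cCa below 8.3. Exposure is also still building early on (2.2.2.1 reports about 3-fold higher AUClast after twelve 5 mg doses), so a Day 3 value would catch only early falls. These points make the gap modest. They do not explain why albumin, which footnote d uses to correct calcium, is drawn on Day 3 without calcium.

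**Conclusion.** The point holds within limits. For asymptomatic cCa of 7.5 to < 8.3 mg/dL, the AE count partly reflects investigator practice. For cCa below 7.5, and for symptomatic cCa below 8.3, it does not. On the phase 2 figures, about 2.8 to 7.1 of 24 treated subjects might have a lowest value of 7.5 to < 8.0. This rests on the constant-hazard scaling and on a longer study with higher doses, so it shows only that the band is unlikely to be empty. It is the number whose status is open, not the error in the AE count.

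A reader might also infer that a numeric withholding limit would settle the count. It would not. Calcium and vitamin D treatment stays with each investigator (3.1) and makes a laboratory change an AE under 9.2.1, and withholding can follow only three of the eight scheduled post-dose results. Counting measured values is the more direct remedy.

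The timing finding is exact: the first on-drug calcium can affect dosing only after 4 of 12 doses. Both parts are cheap improvements, not faults that undermine the trial.

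**What to change.** 1. **SAP 9.6.2.** Add a table, by arm, of the number and percentage of subjects by lowest post-baseline cCa in the three SAP 5.4 bands, plus 8.3 mg/dL and above, whatever action was taken and whether or not an AE was reported. Base it on scheduled values, because unscheduled draws themselves depend on investigator action; list those separately. Treatment can still raise later values, but it cannot remove the low value that prompted it. Cost: one table from data already collected.

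2. **Protocol Table 1b and 7.2.3.** Add calcium to the existing Day 3 predialysis sample. Cost: one extra assay per subject, about 32 in all, with no new visit or draw.

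3. **Secondary safety suggestion, Protocol 6.3.1.1.** State that the next dose is withheld at least when cCa is below 7.5 mg/dL, which 9.3 already makes an SAE, or when hypocalcemia is symptomatic. Add a resume value set by the sponsor, and make the cross-reference in 9.3 point to this text. Cost: wording, and a repeat cCa while dosing is held. This makes dosing more consistent; it does not replace the table in item 1.
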